2. STUDY HYPOTHESIS

We hypothesize that, compared to a conventional dosing regimen (CDR), a repeated bolus dosing regimen (RBDR) of amiodarone will result in an increased percentage of patients who convert to normal sinus rhythm within 24 hours of initial AF.

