3.2 Secondary Objectives

The secondary objectives of this study are:

- Compare the total time, in minutes, during the first 24 hours that the patient achieves target HR (HR < 110 bpm) between patients who receive a repeated amiodarone bolus dosing regimen and those who receive a conventional amiodarone bolus dosing regimen.
- Compare the time to achieve target HR (HR < 110 bpm) between patients who receive a repeated amiodarone bolus dosing regimen and those who receive a conventional amiodarone bolus dosing regimen.

- Compare the time to achieve NSR between patients who receive a repeated amiodarone bolus dosing regimen and those who receive a conventional amiodarone bolus dosing regimen.
- Compare the percentage of patients who achieve NSR by ICU discharge and hospital discharge between patients who receive a repeated amiodarone bolus dosing regimen and those who receive a conventional amiodarone bolus dosing regimen.
- Compare the percentage of patients who have recurrent AF before ICU discharge and before hospital discharge between who patients who receive a repeated amiodarone bolus dosing regimen and those who receive a conventional amiodarone bolus dosing regimen.
- Compare the incidence and severity of hypotension between patients who receive a repeated amiodarone bolus dosing regimen and those who receive a conventional amiodarone bolus dosing regimen.
- Compare the incidence and severity of conduction abnormalities between patients who receive a repeated amiodarone bolus dosing regimen and in those who receive a conventional amiodarone bolus dosing regimen.
- Compare the incidence and severity of amiodarone-related pulmonary fibrosis between patients who receive a repeated amiodarone bolus dosing regimen and those who receive a conventional amiodarone bolus dosing regimen.

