10.3 Postoperative data

- Date/time of ICU admission
- Date/time of extubation

- Date/time of ICU discharge
- Date/time of hospital discharge
- Vasopressor (norepinephrine, vasopressin) use at ICU admission
- Inotrope (dopamine, epinephrine, milrinone, dobutamine) use at ICU admission
- Pacemaker use at ICU admission
- Date/time of first AF
- Presence of rapid ventricular response with first AF
- Heart rate at time of AF diagnosis
- Heart rate at initiation of study group treatment (initial amiodarone bolus)
- Hourly heart rate for 24 hours, beginning at start of study group treatment
- Date/time of study randomization
- Date/time of first study drug administration
- Total number of amiodarone boluses administered
- Restoration of normal sinus rhythm by ICU discharge
- Restoration of normal sinus rhythm by hospital discharge
- Date/time of normal sinus rhythm
- Total number of stable AF episodes (excluding initial episode) prior to ICU discharge
- Total number of stable AF episodes (excluding initial episode) prior to hospital discharge
- Presence of hypotension (SBP < 90 mmHg or increase in vasopressor infusion by 1.5x to achieve SBP > 90 mmHg) after amiodarone therapy during amiodarone IV load period
- Severity of hypotension after amiodarone therapy during amiodarone IV load period
 - Mild: No intervention needed
 - Moderate: Hypotension resolved after fluid bolus

- Severe: Hypotension requiring vasopressor or inotropic therapy
- Very Severe: Hypotension requiring multiple vasopressor or inotropic therapies
- Presence of bradycardia (HR <60 beats per minute) after amiodarone therapy during amiodarone IV load period
- Presence of conduction abnormality during amiodarone IV load period
- Severity of conduction abnormality during amiodarone IV load period
 - Mild: No intervention
 - Moderate: Temporary pacemaker required for ≤ 12 hrs
 - Severe: Temporary pacemaker required for 12-48 hrs
 - Very Severe: Temporary pacemaker required for ≥ 48 hrs or permanent pacemaker required
- Presence of pulmonary fibrosis related to amiodarone therapy
- Severity of pulmonary fibrosis related to amiodarone therapy
 - Mild: No intervention needed
 - Moderate: Discharged on oxygen at night only
 - Severe: Discharged on continuous oxygen
 - Very Severe: Discharged on mechanical ventilation or patient death due to pulmonary fibrosis

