11.3 Secondary Objectives

To assess the secondary objectives, the following statistical analysis plan will be used:

- To compare the total time, in minutes, during the first 24 hours that the patient achieves target HR (HR < 110) between groups, first, the time that each patient has the target HR will be calculated. The total time at target HR will be calculated as the number of hourly HR measures ≤ 100 x 60 minutes. This calculated time data for each group will be will be analyzed for normality. Normal data will be described by the mean and standard deviation; whereas, non-normal data will be described by the median and interquartile range. If one group is normal and one group is non-normal, both groups will be reported as non-normal data. The total time at target HR between groups will then compared with either the 2-tailed, independent samples student t-test (normal data) or with the Mann-Whitney U test (non-normal data).

- To compare the time to achieve target HR (HR ≤ 110 bpm) between patients in each group, the time to achieve target HR will be calculated for each patient. This time will be calculated as the total time, in minutes, between the start of the initial amiodarone bolus and the first recorded HR ≤ 110 bpm. The time to achieve NSR data will be analyzed for normality. Normal data will be described by the mean and standard deviation, whereas

non-normal data will be described by the median and interquartile range. If one group is normal and one group is non-normal, both groups will be reported as non-normal data. The time to achieve NSR will then compared with either the 2-tailed, independent samples student t-test (normal data) or with the Mann-Whitney U test (non-normal data).

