- To compare the time to achieve NSR between patients in each group, the time to achieve NSR will be calculated for each patient. For patients who do not convert to NSR by the time they are discharged from the hospital, the date/time that they achieve NSR will be the date/time of hospital discharge. The time to achieve NSR data will be analyzed for normality. Normal data will be described by the mean and standard deviation, whereas non-normal data will be described by the median and interquartile range. If one group is normal and one group is non-normal, both groups will be reported as non-normal data. The time to achieve NSR will then compared with either the 2-tailed, independent samples student t-test (normal data) or with the Mann-Whitney U test (non-normal data).
- To compare the percentage of patients who achieve NSR by ICU discharge and hospital discharge, the number of patients in each group who have converted to NSR at each time point will be calculated and reported as number and percentage. The number who have achieved NSR will be compared with the Fischer's Exact test or the Chi-Square test, as appropriate.
- To compare the percentage of patients who have recurrent AF before ICU discharge and hospital discharge, the number of AF episodes after the initial AF episode will be counted

for each patient in each group prior to ICU discharge and prior to hospital discharge. The mean (normal data) or median (non-normal data) number of additional AF episodes will be compared between the groups using the 2-tailed, independent samples student t-test (normal data) or with the Mann-Whitney U test (non-normal data).

- To compare the incidence and severity of hypotension, the number of patients who develop hypotension will first be calculated and reported as number and percentage. The number of patients with hypotension will be compared with the Fischer's Exact test or the Chi-Square test, as appropriate . The number of patients who develop mild, moderate, severe or very severe hypotension will then be calculated and reported as number and percentage. The number of patients with each severity class will then be compared between groups using Somers' D test for ordinal data.

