- To compare the time to achieve NSR between patients in each group, the time to achieve NSR will be calculated for each patient. For patients who do not convert to NSR by the time they are discharged from the hospital, the date/time that they achieve NSR will be the date/time of hospital discharge. The time to achieve NSR data will be analyzed for normality. Normal data will be described by the mean and standard deviation, whereas non-normal data will be described by the median and interquartile range. If one group is normal and one group is non-normal, both groups will be reported as non-normal data. The time to achieve NSR will then compared with either the 2-tailed, independent samples student t-test (normal data) or with the Mann-Whitney U test (non-normal data).
- To compare the percentage of patients who achieve NSR by ICU discharge and hospital discharge, the number of patients in each group who have converted to NSR at each time point will be calculated and reported as number and percentage. The number who have

achieved NSR will be compared with the Fischer's Exact test or the Chi-Square test, as appropriate.

- To compare the percentage of patients who have recurrent AF before ICU discharge and hospital discharge, the number of AF episodes after the initial AF episode will be counted for each patient in each group prior to ICU discharge and prior to hospital discharge. The mean (normal data) or median (non-normal data) number of additional AF episodes will be compared between the groups using the 2-tailed, independent samples student t-test (normal data) or with the Mann-Whitney U test (non-normal data).
- To compare the incidence and severity of hypotension, the number of patients who develop hypotension will first be calculated and reported as number and percentage. The number of patients with hypotension will be compared with the Fischer's Exact test or the Chi-Square test, as appropriate . The number of patients who develop mild, moderate, severe or very severe hypotension will then be calculated and reported as number and percentage. The number of patients with each severity class will then be compared between groups using Somers' D test for ordinal data.

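### Time to NSR counts patients who never convert as converting at hospital discharge, so an early discharge in AF ranks better than a later real conversion

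*Protocol*

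**What the plan says.** Protocol 3.2 lists the comparison as a secondary objective: "Compare the time to achieve NSR between patients who receive a repeated amiodarone bolus dosing regimen" and those on the conventional regimen. Protocol 11.3 supplies the rule for patients who leave hospital without converting: "the date/time that they achieve NSR will be the date/time of hospital discharge". SAP 1.3 has the same rule, opening "For patients who do not convert to NSR by the time they are discharged from the hospital, the date/time that they achieve NSR will be" and ending with the discharge time.

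The times are then handled as complete data. They are checked for normality and compared by a two-tailed t-test or by Mann-Whitney. "If one group is normal and one group is non-normal, both groups will be reported as non-normal data". Neither document has a censoring rule, a worst-rank rule, a survival method, or a rule for death in AF.

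Three nearby points are also unsettled:

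- **Start of the clock.** None is stated for time to NSR. The target heart-rate bullet in 11.3 starts at the initial amiodarone bolus, while the hypothesis in Protocol section 2 counts conversion "within 24 hours of initial AF".
- **Patients who never reach target heart rate.** Protocol 10.3 collects "Hourly heart rate for 24 hours, beginning at start of study group treatment", but no rule covers a patient who does not reach target in that window.
- **Variable named.** The target heart-rate bullet, in both documents, says "The time to achieve NSR data will be analyzed for normality". This looks like wording carried over from the neighbouring bullet.

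**The concern.** Discharge in AF is a failure to convert, yet the rule records it as a conversion at a known time. Two orderings go wrong. A patient who leaves early without converting beats a patient who stays and converts later. Among patients who never convert, the one with the shorter stay is scored as the faster converter.

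Length of stay among treatment failures therefore enters a comparison that is meant to be about rhythm. The trial is open-label (Protocol section 4) and postoperative care is at the treating teams' discretion (Protocol section 9), so stay could differ between arms for reasons unrelated to conversion. The test could then reject when conversion is the same in both arms, or miss a real difference. The reported median or mean time to NSR would carry the same distortion.

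**Working it through.** The documents state no power, effect size, conversion rate or length of stay for this endpoint, so there is no planned figure to reproduce. The inputs they do give are 30 patients per arm, a 0.05 significance level, two-tailed tests and the discharge rule. All other inputs below are assumptions.

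**1. Ordering, with no assumptions.** A patient discharged in AF on day 4 is recorded at 4 × 1440 = 5760 min. A patient who truly converts on day 6 is recorded at 6 × 1440 = 8640 min. The non-converter has the shorter time and the better rank.

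**2. A worked pair of arms.** In arm A, 15 convert on day 1 and 15 leave in AF on day 3. In arm B, 15 convert on day 1 and 15 convert on day 5. True conversion is 15/30 v 30/30.

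- Plan: the means are (15×1 + 15×3)/30 = 2.0 days and (15×1 + 15×5)/30 = 3.0 days. Of 30 × 30 = 900 pairs, A is better in 225 + 225 and tied in 225, so U = 450 + 112.5 = 562.5 against an expected 450.
- The tie-corrected variance is (900/12) × [61 − (26970 + 3360 + 3360)/(60×59)] = 3861, SD 62.1. Then z = (112.5 − 0.5)/62.1 = 1.80 and p = 0.071, in favour of A.
- Worst rank: A is better in 225 pairs and tied in 225, so U = 337.5. The distance from 450 is the same, p = 0.071, now in favour of B.

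The direction of the result reverses.

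**3. False rejection when conversion is identical.** Simulation of 6000 trials per scenario. Assumed: conversion time log-normal, median 12 h, log SD 1; non-converter discharge time log-normal, log SD 0.3. The plan's normality check was applied (Shapiro-Wilk p > 0.05 in both arms leads to the t-test). It chose the t-test in at most 0.02% of trials, so the working test is Mann-Whitney.

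| Never convert (both arms) | Median stay of non-converters | Rejection under the plan |
|---|---|---|
| 40% | 5 v 7 days | 9.6% |
| 30% | 5 v 7 days | 6.6% |
| 20% | 5 v 7 days | 5.2% |
| 10% | 5 v 7 days | 5.0% |
| 40% | 5 v 6 days | 6.7% |
| 30% | 5 v 6 days | 5.0% |
| 40% | 5 v 5 days | 5.0% |

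With a tied worst rank, rejection is 4.6% to 5.5% throughout. The simulation standard error is about 0.3 points near 5%. Repeat runs of the first row gave 8.4% and 9.5%.

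**4. Slower conversion.** With the median raised to 72 h, stays of 5 v 7 days, and conversions after discharge counted as non-conversion, rejection under the plan is 10.7% at 10% never converting and 15.2% at 20% (a repeat of the latter gave 14%).

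**5. Power when RBDR truly lowers non-conversion from 45% to 25%** (12 h median).

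| Median stay of non-converters, RBDR v CDR | Plan | Tied worst rank |
|---|---|---|
| 5 v 5 days | 24% | 26–27% |
| 6 v 5 days | 17% | 26–27% |
| 7 v 5 days | 13% | 26–27% |
| 8 v 5 days | 11% | 26–27% |
| 5 v 7 days | 42% | 27% |

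The last row shows the rule inflating rejection in favour of RBDR when the stay difference runs the other way.

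**6. A second model, with a censored log-rank test added.** 3000 trials per scenario; conversion times exponential, discharge day normal with SD 2 days and drawn independently of conversion.

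| Scenario | Plan (Mann-Whitney) | Worst rank | Log-rank, censored |
|---|---|---|---|
| No difference, median 24 h, 40% never convert, mean stay 5 v 7 days | 10.4% | 4.7% | 4.9% |
| No difference, median 72 h, 30% never convert, mean stay 5 v 7 days | 21.8% | 6.2% | 4.9% |
| 40% v 10% never convert, median 24 h, equal stay (7 days) | 49.7% | 51.6% | 69.4% |
| 40% v 10% never convert, median 72 h, equal stay (7 days) | 30.1% | 36.5% | 43.7% |

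**The case against.** The strongest reply is that the rule is crude but rarely matters.

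- With conversion as fast as a 12 h median, only about 1% of converter/non-converter pairs are actually inverted. Most of the quantified harm comes from an assumed difference in stay among failures.
- Nothing in the documents supports 30–40% of patients never reaching NSR by discharge, or stays that differ by one or two days. Both arms receive the same infusion and continued loading.
- With equal stays the test holds its level and loses only 2 to 3 points of power (24% v 26–27%).
- The distortion has no known direction.
- The primary 24-hour proportion and the stop-or-extend rule do not use this endpoint. The separate proportions in NSR at ICU and hospital discharge would show how many never converted.
- The hypothesis concerns the primary endpoint, so it does not contradict the clock for this one.

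Most of this stands as a limit on size. The inflation is assumption-driven and can favour either arm, and the clock is unstated rather than contradictory. It does not rescue the rule. The mis-ordering needs no assumption, and the discharge proportions do not correct the p-value or the median for time to NSR. Nor is the effect always negligible when few fail to convert: the near-nominal level at 20% or fewer holds for the 12 h median and fails at 72 h.

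**Conclusion.** The concern holds. The rule as written scores discharge in AF as a conversion, and nothing elsewhere in the Protocol or SAP undoes it. That part is certain.

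Its size is not known. Under the assumptions shown, false rejection ranges from nominal (equal stays, or 20% or fewer never converting at a 12 h median with stays of 5 v 7 days) to about 10% (40% never converting, stays of 5 v 7 days). It reaches 15–22% when conversion is slow, 20–30% never convert and stays differ by two days. Power for a real benefit can fall or be artificially raised, depending on which arm's non-converters stay longer.

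The damage is confined to one secondary endpoint. It should still be corrected before the data are analysed, because choosing the handling of non-converters afterwards would be a post hoc decision on an efficacy result.

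**What to change.** In Protocol 11.3 and SAP 1.3, delete the rule that sets time to NSR to the discharge time, and pre-specify one of these:

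- **Preferred, smallest change:** keep the two-sided Mann-Whitney test, with every patient who has not converted by discharge, including deaths in AF, sharing one tied worst rank. Drop the mean and t-test option for this endpoint.
- **Alternative:** a time-to-event comparison (Kaplan-Meier, log-rank) censored at discharge, with deaths in AF kept as never converting. It had more power in the second model, but that model made discharge independent of conversion. The plan must state the assumption that discharge in AF is uninformative.

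State the start of the clock. The start of the initial amiodarone bolus matches the target heart-rate bullet. Randomization time is also collected and would be defensible, but one origin must be named. Apply the same handling to patients who never reach target heart rate in the hourly readings, and correct that bullet so the variable analysed is time to target heart rate.

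The cost is wording only. Protocol 10.3 already collects the date/times of NSR, randomization, first study drug and hospital discharge, and NSR status at discharge. With the worst rank, no mean time to NSR can be reported, and the median is not reached in an arm where half or more never convert.

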1. BACKGROUND

Atrial fibrillation (AF) is a common complication following cardiac surgery, occurring in approximately 33% of all patients after cardiac surgery. AF can sometimes cause a rapid ventricular rate (RVR), defined as a HR greater than 110 beats per minute (BPM). AF is typically characterized as either stable (systolic blood pressure (SBP) \geq 90 mmHg) or unstable (SBP <90 mmHg). Patients with unstable AF with or without RVR may require immediate electrical cardioversion to restore normal sinus rhythm (NSR) and an appropriate blood pressure; whereas, patients with stable AF frequently undergo medical therapy to either treat RVR or to restore NSR.

Amiodarone is a class III antiarrhythmic with beta-blocker activity that also blocks myocardial potassium, sodium and calcium channels. In stable AF, amiodarone is frequently given to control the HR and restore NSR after cardiac surgery. In this setting, amiodarone is commonly given as an initial intravenous (IV) bolus (150 mg IV) followed by a combined IV and oral load to a total dose of 8 gm. Because of amiodarone's beta-blocker activity, the IV bolus is associated with a reduced HR and may lead to restoration of NSR on its own. For this reason, some clinicians will provide up to 5 additional IV amiodarone boluses during the drug's loading period to treat RVR. Other clinicians will not specifically treat RVR in stable AF and will continue with the routine amiodarone IV and oral load. At this time, both dosing regimens are routinely used for patients after cardiac surgery, the decision to use one over the other is made based on clinician preference. It is not known whether the repeated amiodarone dosing regimen is better than the conventional amiodarone dosing regimen with regard to successful conversion to NSR or the time to conversion to NSR in patients with stable AF.

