10. DATA COLLECTION

Preoperative, intraoperative, and postoperative data will be recorded and entered in the appropriate data collection sheets for all randomized patients. Study data will not be collected on non-enrolled patients or enrolled patients who are not randomized. Data will include, but is not limited to, previously-obtained preoperative, intraoperative, and postoperative data, concomitant procedures, procedure related complications and adverse events. All study data will be maintained on a REDCap database and will only be accessed for study purposes. A list of the data to be collected is provided below:

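### The recurrent-AF count scores 0 for patients who never leave AF, and its data fields list only stable episodes, so it can mislead if the arms differ in conversion or in unstable recurrences

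*Protocol*

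**What the plan says.** The objective in Protocol 3.2 is to "Compare the percentage of patients who have recurrent AF before ICU discharge and before hospital discharge" between the two regimens. Protocol 11.3, repeated in SAP 1.3, puts this into practice by a count: "the number of AF episodes after the initial AF episode will be counted" for each patient in each group, up to ICU discharge and up to hospital discharge. The groups are then compared by t-test or Mann-Whitney U. The count is not restricted to patients who reached sinus rhythm, and neither document defines a recurrence.

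The data items that would feed the count are in Protocol 10.3: "Total number of stable AF episodes (excluding initial episode) prior to ICU discharge" and "Total number of stable AF episodes (excluding initial episode) prior to hospital discharge". Protocol 1 classes AF as stable "or unstable (SBP <90 mmHg"). Protocol 9 also treats as unstable a patient who needs an increase of more than 1.5x in vasopressor infusion to hold blood pressure.

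Two other places bear on the point. Protocol 11.3 foresees non-conversion ("For patients who do not convert to NSR by the time they are discharged from the hospital"), but the rule it gives there is for time to NSR only. It also has a separate secondary analysis, "To compare the percentage of patients who achieve NSR by ICU discharge and hospital discharge".

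**The concern.** Only a patient who has left AF can have a later episode, so the count mixes two things: how many patients converted, and how often converters relapsed. The poorest rhythm course, unbroken AF to discharge, gets the best possible score. A regimen that converts more patients puts more of them at risk of relapse and can be charged with more recurrence for that reason alone. The trial's hypothesis (Protocol 2) is that RBDR converts more patients within 24 hours. If some of that gap lasts to discharge, this comparison would lean against RBDR.

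The restriction to stable episodes can act in either direction. A recurrence with low blood pressure, or one needing a large vasopressor increase, is still AF by the protocol's own classification but has no listed field. If such recurrences are more frequent in one arm, that arm's recorded count falls further below its true count.

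Both features remain whether the result is expressed as a percentage of patients, as in 3.2, or as a mean or median count, as in 11.3. That mismatch is a separate matter, and resolving it would cure neither feature.

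**Working it through.** The documents state no conversion rate, recurrence rate or power for this endpoint, so there is no figure to reproduce. The only input taken from them is the planned 30 patients per group (Protocol 11, SAP 1). All rates below are assumptions.

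**1. Patients who never convert**

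Formulas, over all randomised patients:
- Share scored as recurrent = P(convert) × P(relapse given conversion).
- Share in recurrence-free sinus rhythm = P(convert) × (1 − P(relapse given conversion)).

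Base case: conversion 50% CDR v 80% RBDR, relapse 30% in both arms.
- Recurrent: 0.50 × 0.30 = 15% v 0.80 × 0.30 = 24%, or 4.5 v 7.2 patients of 30.
- Recurrence-free sinus rhythm: 0.50 × 0.70 = 35% v 0.80 × 0.70 = 56%.

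The two summaries point in opposite directions although relapse risk among converters is identical.

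The next table gives the chance that RBDR has more recurrent patients than CDR, from two independent binomials of 30, calculated exactly:

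| Conversion CDR v RBDR | Relapse, both arms | Recurrent | Recurrence-free NSR | RBDR higher | CDR higher |
|---|---|---|---|---|---|
| 80% v 80% | 30% | 24% v 24% | 56% v 56% | 44% | 44% |
| 60% v 70% | 30% | 18% v 21% | 42% v 49% | 55% | 32% |
| 50% v 80% | 30% | 15% v 24% | 35% v 56% | 77% | 15% |
| 40% v 90% | 40% | 16% v 36% | 24% v 54% | 95% | 2% |

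The remainder in each row is ties. The second and fourth rows are the extremes over conversion 40-60% v 70-90% and relapse 30-40%, so the range is 55-95%. The first row is the reference: with identical arms RBDR is already numerically higher in 44% of trials.

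Numerically higher is not the same as significant. Simulated Mann-Whitney tests on counts (Poisson recurrences among converters, 0 for non-converters, 30% relapse in both arms) gave p<0.05 against RBDR in 11.3% of trials at 60% v 90% conversion, 4.5% at 80% v 90%, and 2.0% at 90% v 90%. The nominal figure is about 2.5% per side.

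The comparison can also run against a real benefit. With conversion 60% v 90% and relapse 30% v 25%, recurrence is 0.60 × 0.30 = 18% v 0.90 × 0.25 = 22.5%.

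**2. Unstable recurrences**

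Recorded recurrence = true recurrence × (1 − share of recurrences that are unstable), if only the listed fields are filled.
- Equal shares, say 20% in both arms, with true recurrence 30%: 0.30 × 0.80 = 24% in both arms. The level is understated but the comparison is not tilted.
- Unequal shares, say 10% CDR v 40% RBDR, same true recurrence: 0.30 × 0.90 = 27% v 0.30 × 0.60 = 18%.

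The second line shows direction only. No passage suggests a split of that size.

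**The case against.** The strongest reply is that recurrence over all randomised patients is a legitimate measure. It preserves randomisation and answers the question in Protocol 3.2 as worded. A patient in unbroken AF has not recurred, so 0 is literally correct. Non-conversion is reported at the same two time points through NSR by ICU and hospital discharge. All of this stands, and a reader who infers that the objective cannot be answered goes too far. What remains is that two results side by side let a reader notice the problem but do not correct the recurrence comparison, and nothing in the plan says the two must be read together.

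The second reply concerns timing. Protocol 2 hypothesises a conversion gap at 24 hours, whereas this endpoint runs to ICU and hospital discharge, and both arms continue the same load after the first day. A reader might infer that the comparison is bound to go against RBDR. The documents do not support that, because no conversion gap at discharge is claimed anywhere, and with equal conversion this bias is absent.

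The third reply concerns the stable limit. A reader might infer that the plan sets a rule scoring unstable recurrences as 0. It does not: 11.3 and SAP 1.3 count AF episodes without qualification, only the field labels in 10.3 say stable, and Protocol 10 says of the list "Data will include, but is not limited to". So this is a conflict between passages. It still matters, because an open-ended list does not create a field, and data collected as listed would miss these episodes. The hypotension item does not fill the gap, since it covers only the IV load period and is not tied to AF recurrence. Against a large effect, the extra boluses are confined to the first 24 hours, while recurrence is followed to hospital discharge.

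**Conclusion.** Both features are in the text. The score of 0 for unbroken AF follows from the counting rule, and no passage overrides it. The stable-only fields conflict with the unrestricted wording of the objective and analysis, and those passages must be reconciled.

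The effect on the comparison is conditional. It needs a difference between arms in conversion by ICU or hospital discharge, or in the share of recurrences that are unstable. On the assumed rates, the chance that RBDR looks numerically worse at equal relapse risk is 77% in the base case and 55-95% over the span examined, against 44% for identical arms. None of these rates comes from the documents. The two effects depend on different unknowns and cannot be assumed to cancel.

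This is a secondary endpoint and the primary analysis is untouched. The change is worth making because it is cheap and the present comparison could be read as evidence about which regimen does better on rhythm.

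**What to change.** - **Protocol 10.3:** delete the word stable from both recurrence items, so that every AF recurrence before ICU discharge and before hospital discharge is counted, and add a stable/unstable flag. Do this before data are collected if possible, since unrecorded episodes may be hard to recover.
- **Protocol 11.3 and SAP 1.3:** keep recurrence over all randomised patients as the answer to the objective in 3.2, and state that patients who never convert contribute 0.
- **Same sections:** add a between-arm comparison, by Fisher's exact or chi-square test, of the proportion converted and free of recurrent AF at ICU discharge and at hospital discharge. Include all randomised patients, with never converted or recurred both counted as failure. Base any conclusion about which arm does better on rhythm on this comparison.
- **Same sections:** report recurrence among converters descriptively. The combined outcome can hide a true excess of relapse in an arm that converts more, and converters are not a randomised subset.

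The cost is two reworded data items, one flag and one added analysis. Continuous ECG monitoring is already standard after surgery (Protocol 9), and NSR by each discharge is already recorded. The downside is one extra secondary comparison that overlaps with NSR by discharge. No treatment or patient management changes.
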